Martini et al. 2016; Rob et al. 2017; Moore et al. 2015) Due to the potential to reduce the radiation dose to less than 1/30 of a standard-dose CT while still providing acceptable image quality with the latest generation of devices, ULDCT of the chest is emerging as an interesting alternative to conventional chest X-ray.

To the best of the authors' knowledge, there are currently no studies comparing and evaluating ultra-low-dose-CT as a primary imaging alternative to chest X-ray in emergency department patients.

[figure not shown]
[figure not shown]
This study aims to compare ULDCT and plain film of the chest with regard to their accuracy in an unfiltered patient cohort of an emergency department. For this purpose, our ULDCT protocol will use the lowest possible dose at which image quality is diagnostically sufficient (approximately 0.2 mSv effective dose). This corresponds to less than 1/30 of the radiation dose of a standard-dose CT of the chest and to only about 2.5 times the dose of a chest X-ray in two views. This dose is equal to less than a month of natural background radiation in Austria and less than the radiation exposure on an intercontinental flight. (Bundesministerium für Arbeit, Soziales, Gesundheit und Konsumentenschutz 2018b; Bundesministerium für Arbeit, Soziales, Gesundheit und Konsumentenschutz 2018a; Ditto et al. 2013)

[figure not shown]
In addition to the accuracy of ULDCT of the chest compared to plain film of the chest, this trial also aims to analyze the clinical relevance of both methods by assessing the respective impact on final diagnosis, as well as possible changes in therapy.

5 Study Design

Study Type	Interventional
Primary Purpose	Diagnostic
Number of Arms	2
Masking (prospective)	None (open label)
Allocation	Randomized
Enrolment	250

Arms	Assigned Interventions

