
Reporting-order: Plain Film - ULDC
 
The plain film of half the participants (randomized) will be submitted for reporting by a radiologist as a first imaging method. After finishing this report, the same radiologist will assess the ULDC of this participant. In this second report, the findings of both examinations will be summarized, and a second report will be filed.
 
Emergency physicians will first receive the report for the plain film of the chest and will be asked for the diagnosis and its probability. Next, the report for ULDC will be presented to them. Again, diagnosis and probabilities will be documented.
	
Diagnostic Test: ULDC
 
Ultra-Low-Dose-CT (ULDC) of the chest using tin filters with third-generation dual-energy CT devices. The projected dose used will be approximately 0.2 mSv per ULDC of the chest.

Reporting-order: ULDC - Plain Film
 
For half the participants (randomized) radiologists will first receive the data from ULDC of the chest and write a report. Subsequently, they will receive the data from the plain film of the chest and may expand their report (explicitly separated).
 
Emergency physicians will first receive the report for the ULDC of the chest and will be asked for probabilities of the nine most frequent diagnoses in chest-imaging plus "other". Next, they will be presented with the report for the plain film and will again be asked to give an estimation of the probabilities for the same diagnoses as before.
	
Diagnostic Test: ULDC
 
Ultra-Low-Dose-CT (ULDC) of the chest using tin filters with third-generation dual-energy CT devices. The projected dose used will be approximately 0.2 mSv per ULDC of the chest.

6 Hypotheses and outcome measures

Null hypothesis:

- There is no difference in accuracy between ULDCCT of the thorax and plain film of the thorax regarding the primary diagnosis.

Alternative hypothesis:

- ULDCCT of the thorax offers higher accuracy than plain film of the thorax regarding the primary diagnosis.

Primary Outcome Measure:

Accuracy of ultra-low-dose-CT of the chest and plain film of the chest

Description:

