Initial radiologic diagnostic accuracy of both methods will be assessed by analyzing the number of reports that are changed after the images of the second modality become available to the radiologist in Arm 1 compared to Arm 2.

In a final approach, the diagnostic accuracy will be analyzed by retrospectively comparing all reports with the gold standard, which will be built from all available patient data at the end of the study, including all follow-up imaging studies and laboratory tests.

Secondary Outcome Measures:

- Sensitivity and specificity in ULDCT and plain film
- Frequency of change in radiological diagnosis
- Frequency of change in emergency physician's diagnosis
- Frequency of change in (planned) therapeutic course of action by emergency physician
- Frequency of accidental diagnosis in ULDCT of the chest and plain film of the chest
- Frequency of additional diagnostic imaging needed
- Frequency of unclear reports in ULDCT and plain film
- Diagnostic confidence in ULDCT and plain film by radiologist
- Diagnostic confidence in ULDCT and plain film by emergency physician

7 Inclusion criteria

Sex	All
Gender-based	No
Age limits	Minimum: 18 years Maximum: 92 years
Accept healthy volunteers	No
Participants	All patients who are assigned to a clinically indicated chest X-ray by the emergency department of Vienna General Hospital
Consent	Ability to provide informed consent Informed consent after detailed patient briefing

8 Exclusion criteria

Clinical status	A critical clinical condition that does not allow the examination with both modalities (ULDCT of the chest, chest X-ray)
Assignment	Assigned to chest X-ray as follow-up
Pregnancy	Women with positive β -HCG-test

9 Ethical considerations

- The mean effective dose of a chest X-ray examination in two views (pa, lat) is 0.08 mSv (Wachabauer and Röthlin 2017).
- The targeted mean effective radiation dose for one thoracic ultra-low-dose-CT (ULDCT) is approx. 0.2 mSv. This corresponds to approximately one month of natural background radiation in Austria. Compared to standard-dose CT examinations, ULDCT of the thorax causes about one-twentieth to one-fortieth of effective radiation dosage. Therefore, its dosage is much closer to a chest X-ray in two views than to a standard-dose CT, or even a low-dose CT examination.
- Even the cumulative dose of both examinations comes with a negligible radiation dose. Thus, no negative effects are to be expected.

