- A delay in diagnosis can be ruled out since each examination is promptly evaluated – before the examination for the second imaging modality is performed.
- Since no contrast medium is applied, adverse effects or events – in this context – can be ruled out.

10 Recruitment

All patients who are assigned to receive a clinically indicated chest X-ray by the emergency department of Vienna General Hospital – regardless of indication – are offered participation in this trial. Thus, only clinically indicated cases may be included.

Patients who meet the eligibility criteria and provide informed consent become participants in this trial and receive an ultra-low-dose-CT examination of the thorax in addition to a chest X-ray.

11 Study duration

Based on a preliminary analysis of frequency, the anticipated total study duration, including analysis of all parameters, is one year.

12 Radiation dose

- Chest X-ray: The reference dose for a chest X-ray in two views is approx. 0.08 mSv (effective dosage) (Wachabauer and Röthlin 2017).
- Thorax-ULDCT: based on recent publications regarding imaging in emphysema and dyspnea, as well as on measurements with a thorax-CT test-phantom performed with the specific CT devices used for the study (Siemens Somatom Drive and Siemens Somatom Force), an effective dose of approx. 0.2 mSv (corresponding to DLP 12.5) appears to be optimal for ULDCT (lowest dose possible with sufficient image quality). This dose is below the effective dose of one month of natural background radiation, which is referenced as 0.23 mSv per month in Austria (2.8 mSv per year). (Bundesministerium für Arbeit, Soziales, Gesundheit und Konsumentenschutz 2018a; Bundesministerium für Arbeit, Soziales, Gesundheit und Konsumentenschutz 2018b; Ditto et al. 2013)

The thorax-CT test-phantom used is model RS-111 by "Radiology Support Devices", Long Beach, California, USA.

13 Radiological analysis

Rationale behind the study design:

Prospective:

For ethical, practical, and legal reasons, the emergency physician always needs an immediate consensus report on both methods written by a single specialist in radiology in order to make a final treatment decision. This would not be possible without a significant delay, if two radiologists had to create two separate reports. The frequency with which diagnoses and therapies by radiologists and emergency physicians differ between Arm 1 and Arm 2 will be measured.

Retrospective:

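### The primary outcome assesses initial accuracy by a changed-report count with no reference standard, and the gold-standard comparison is not designated, with its reading set, as the one test of the null

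*Combined protocol and SAP*

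**What the plan says.** Section 6 states the null as "There is no difference in accuracy between" ULDCT and plain film for the primary diagnosis, with a one-sided alternative favouring ULDCT. The primary outcome is accuracy, and its description has two parts:

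- Initial accuracy is assessed by "analyzing the number of reports that are changed after the images of the second modality become available to the radiologist in Arm 1" against Arm 2.
- "In a final approach, the diagnostic accuracy will be analyzed by retrospectively comparing all reports with the gold standard", which is built from all patient data available at the end of the study.

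The secondary outcomes in the same section include "Frequency of change in radiological diagnosis".

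Section 5 describes the prospective readings, which are open label. One radiologist reports the first modality and then sees the other. For Arm 1, "In this second report, the findings of both examinations will be summarized, and a second report will be filed". Section 9 says that each examination is evaluated "before the examination for the second imaging modality is performed".

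Section 13 describes a separate retrospective exercise. Eight readers report every examination in structured form, one modality of a patient at a time, with at least a month between the two reading rounds. Their findings are set against the gold standard, and the stated purpose is to establish accuracy, sensitivity and specificity.

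Section 14 assumes accuracies of 80% and 93% and gives 123 per arm for 85% power at one-sided 2.5%. It assigns chi-square tests to percentages in general and names no primary comparison.

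**The concern.** A changed report shows that the reader revised an opinion, not that the first opinion was wrong. The count depends on how often the modalities disagree and on which one the reader then believes. A reader who tends to trust CT will change more reports when film comes first, even if the two methods are equally accurate. Section 6 nevertheless offers this count as a measure of accuracy under the primary outcome.

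The gold-standard comparison does measure accuracy, but two things about it are open. No section says that it alone decides the null. Its readings are also unsettled: Section 6 takes all reports, which could include second reports made with both modalities in view, while Section 13 takes the eight readers' structured findings. With two measures under one primary outcome and more than one candidate set of readings, the deciding analysis could be chosen after the results are known.

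**Working it through.** **1. The plan's own figure.** Inputs from Section 14: p1 = 0.80, p2 = 0.93, one-sided alpha 0.025, power 0.85. Pooled formula for two independent proportions, with mean p = 0.865:

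n = [1.960·√(2·0.865·0.135) + 1.036·√(0.80·0.20 + 0.93·0.07)]² / 0.13² = 122.5, so **123 per arm**.

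Power at 123 = Φ{[0.13·√123 − 1.960·√(2·0.865·0.135)] / √(0.80·0.20 + 0.93·0.07)} = Φ(1.04) = 85.1%. At 122 it is 84.9%. The figure reproduces as an unpaired two-group comparison.

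**2. Which analysis this matches.** It matches first reports, Arm 1 plain film v Arm 2 ULDCT. It also matches the count in one special case: a report changes exactly when the first report was wrong (20% v 7% changed, power 85.1%). It does not match the eight-reader exercise, where every patient has both modalities read. As a simple paired illustration, take one reading per patient and modality and independent errors (assumed). The discordance is then ψ = 0.80·0.07 + 0.93·0.20 = 0.242, and McNemar's test needs [1.960·√0.242 + 1.036·√(0.242 − 0.13²)]² / 0.13², or 126 patients in total. Reader variance would have to be added, and the documents do not give it.

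**3. The count when accuracy is equal.** The documents do not give reader behaviour or error correlation, so both are assumed here. A disagreement means that exactly one modality is wrong. With common accuracy a and independent errors, disagreements have probability D = 2a(1 − a), half with film wrong and half with ULDCT wrong. A share q is resolved correctly. Of the rest, 75% go to ULDCT.

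- Arm 1 changes = q·D/2 + (1 − q)·0.75·D
- Arm 2 changes = q·D/2 + (1 − q)·0.25·D

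Example, a = 0.80 (D = 0.32), q = 0.5: Arm 1 = 0.08 + 0.12 = 0.20 and Arm 2 = 0.08 + 0.04 = 0.12. The rejection rate is Φ{[0.08·√123 − 1.960·√(2·0.16·0.84)] / √(0.20·0.80 + 0.12·0.88)} = Φ(−0.25) = 40%.

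| q | Changed, both 80% accurate (Arm 1 v Arm 2) | Rejects | Changed, both 93% accurate (Arm 1 v Arm 2) | Rejects |
|---|---|---|---|---|
| 0 | 24.0% v 8.0% | 93% | 9.8% v 3.3% | 54% |
| 0.25 | 22.0% v 10.0% | 73% | 9.0% v 4.1% | 34% |
| 0.5 | 20.0% v 12.0% | 40% | 8.1% v 4.9% | 18% |
| 0.75 | 18.0% v 14.0% | 13% | 7.3% v 5.7% | 7% |
| 1 | 16.0% v 16.0% | 2.5% | 6.5% v 6.5% | 2.5% |

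The nominal rate is 2.5%. If errors are correlated at 0.5, D halves, and the q = 0 rates fall to 64% (both 80%) and 30% (both 93%).

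**4. The count when accuracy truly differs (80% v 93%).** P(film wrong, ULDCT right) = 0.20·0.93 = 0.186 and P(film right, ULDCT wrong) = 0.80·0.07 = 0.056. If every disagreement is resolved correctly, the arms show 18.6% v 5.6% changed and power is 88%, so the count works. If disagreements are instead split evenly whichever modality is right, both arms show 0.242/2 = 12.1% and the count rejects in only 2.5% of trials despite a 13-point difference.

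**The case against.** The strongest reply is that the plan already points to the right analysis. The null is about accuracy, Section 6 calls the count initial and the gold-standard comparison final, and Section 13 says that the latter is there to establish accuracy. This largely stands. A reader might infer that no reference-standard analysis is planned, and the documents do not support that. The gap is one of designation and reading set. On the reading set, it is also natural to take the retrospective reports in Section 6 as the eight readers' single-modality reports, but the text does not settle it.

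It can also be said that radiologists will often recognise the better image. They will, and the size shrinks accordingly. With no correct recognition, the count rejects more often at equal 80% accuracy (93%) than at a true 80% v 93% (83%), and a reader might infer that it ranks the two situations backwards. That needs readers with no ability to pick the correct modality. Once a quarter of disagreements are resolved correctly, the figures are 73% and 85%. The model also leaves out cases where both readings are wrong but differ, although Section 5 allows nine diagnoses plus a residual category.

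Finally, a reader might infer from Section 5 that changes are recorded differently by arm, since Arm 1 files a summarising second report and Arm 2 allows an optional addition. Section 13 requires a consensus report on both methods without distinguishing arms. Differential recording is therefore possible but not documented, and the point does not rest on it.

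**Conclusion.** The concern holds in this form. The changed-report count, as written under the primary outcome, is not a valid test of the accuracy null unless disagreements are resolved to the correct side. Under the assumed 75% lean to ULDCT and independent errors, false rejection runs from 2.5% (all resolved correctly) through 40% (half) to 93% (none) when both methods are 80% accurate, and from 2.5% through 18% to 54% when both are 93% accurate. Only the accuracies, the alpha and the 123 per arm come from the plan. The behaviour and the error correlation are assumptions, so the range matters more than any single figure.

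Separately, the gold-standard comparison is planned but is not designated the single confirmatory test, and its reading set is not fixed. The figure of 123 per arm is arithmetically correct for an unpaired comparison. It does not show which analysis was intended, and it does not describe a paired eight-reader analysis.

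**What to change.** In Sections 6 and 14:

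1. Move the changed-report count out of the primary outcome to the secondary outcome already listed, "Frequency of change in radiological diagnosis", as a descriptive measure, with a change defined identically in both arms.
2. State that the null is tested by one gold-standard comparison at one-sided 2.5%, on single-modality readings only. Exclude second reports made with both modalities in view.
3. Name the reading set and a test that matches it, and report the other set as supportive. There are two defensible choices:
   - First prospective reports, Arm 1 plain film v Arm 2 ULDCT, unpaired. This is the comparison that 123 per arm powers at 85%.
   - The eight readers' structured findings, with a paired multi-reader analysis and its own power statement. These readings are independent and anonymised.

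The choice is the sponsor's, and it should be made before results are seen.

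The change is to wording and needs no extra patients or examinations. It has three costs. The headline result waits for the gold standard. If first reports are chosen, they need a scoring rule for the primary diagnosis, because structured reporting is specified only for the retrospective readings. And because the gold standard draws on all imaging results, a possible lean towards ULDCT should be acknowledged under either choice.

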This will involve a multi-reader analysis by four radiologists in training and four specialists. All eight physicians will independently read and report all examinations by means of structured reporting. The reading time is not specified. Two groups with all 300 patients each will be created: In the 1st group, the chest X-ray examinations of Pts. 1-150 and the Ultra-Low-Dose-CT examinations of Pts. 150-300 will be available. In the 2nd group, this will be reversed. All patients will be fully anonymized and randomized. Two radiologists in training and two specialists will first read and report on group 1, the other four doctors will first read and report on group 2. Between the evaluations of group 1 and group 2 there will be at least one month to prevent a possible recognition of a case.

The gold standard will be built from all available patient data at the end of the study, including the results of all imaging procedures, follow-up examinations, physical medical examinations, laboratory and histopathological tests and further diagnostic procedures (concerns all available data, regardless of whether the patient is admitted as an inpatient).

The structured findings are then compared with the gold standard to determine the accuracy, sensitivity and specificity of both procedures.

Documentation:

- Waiting time for the ULDCT will be logged.
- Waiting time for the X-ray will be logged.

14 Statistical analysis plan

Power and sample size:

A total of 250 participants is targeted.

This is based on the following assumptions:

- Accuracy of a chest X-ray is 80%
- Accuracy of a ULDCT of the chest is 93%
- Dropout rate is 20% (one in five potential participants)

According to calculations using NQuery Advanced (version 8.3.0.0), 123 participants per arm (total of approx. 250 participants) will be required to reach a power of 85% in a one-sided test (alpha 2.5%). Due to the assumption of a dropout rate of 20% (approx. one in five potential participants), a sample size of 300 is required.

Cross tabulation and χ^2 -tests will be used to compare percentages (e.g., accuracy, sensitivity, ...). Diagnostic confidence will be compared by applying a Mann-Whitney U test.

15 Compensation

None.

Participants will not receive any compensation.

16 Study suspension

Since no negative effects on patients are expected, the trial will be suspended or stopped only if it becomes obvious that ultra-low-dose-CT examinations do not offer any benefit.

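### Emergency physicians' diagnoses are analysed only as a frequency of change and never scored against the gold standard, so the analysis cannot show whether either modality made them better or worse

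*Combined protocol and SAP*

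**What the plan says.** Section 4 (Background and summary) sets, beside accuracy, the aim to "analyze the clinical relevance of both methods by assessing the respective impact on final diagnosis", and also mentions possible changes in therapy.

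Section 5 (Study Design, arms table) randomises the reporting order. The physician responds after the first report alone and again after the second. In the plain-film-first arm the response is a diagnosis and its probability. In the ULDCT-first arm the physician "will be asked for probabilities of the nine most frequent diagnoses in chest-imaging", plus an 'other' category. I call these Arm 1 and Arm 2, in the order listed.

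Section 6 lists three physician outcomes, all secondary:
- "Frequency of change in emergency physician's diagnosis"
- "Frequency of change in (planned) therapeutic course of action by emergency physician"
- "Diagnostic confidence in ULDCT and plain film by emergency physician"

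The gold standard is applied elsewhere. Section 6, under the primary outcome, says that "the diagnostic accuracy will be analyzed by retrospectively comparing all reports with the gold standard". Section 13, after describing the eight-reader study, says: "The structured findings are then compared with the gold standard to determine the accuracy, sensitivity and specificity of both procedures".

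Section 13 also says that the frequency with which radiologists' and emergency physicians' diagnoses and therapies differ between the arms will be measured. Section 14 names chi-square tests for percentages and a Mann-Whitney test for confidence. It defines no analysis of physician accuracy.

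**The concern.** Section 5 places the physician in a randomised comparison: one group has seen only the plain-film report when first asked, the other only the ULDCT report. A gold standard is to be built for the patients. The two are never brought together.

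A change count records that the second report moved the physician, not whether the move was right. It also depends on how far physicians trust each modality, and they know which one they are reading because the trial is open label. A high change rate after ULDCT could mean corrected errors, new errors, or both. The aim of describing clinical relevance through final diagnosis would then rest on a measure that cannot tell these apart.

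**Working it through.** **1. What is scored against the gold standard**

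| Item | Source | Scored? |
|---|---|---|
| Radiology reports | Section 6, primary outcome | Yes |
| Structured findings of eight readers | Section 13 | Yes |
| Physician diagnosis after first report | Section 5 | No |
| Physician diagnosis after second report | Section 5 | No |
| Change in physician diagnosis, change in therapy, confidence | Section 6 | Not measures of correctness |

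In Section 5 physicians receive reports and give diagnoses, so the reports named in Section 6 are radiological ones.

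**2. The plan's sample size**

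Inputs (Section 14): 80% v 93%, one-sided alpha 2.5%, power 85%. With mean proportion 0.865 and the pooled formula without continuity correction:

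n = [1.960 × √(2 × 0.865 × 0.135) + 1.036 × √(0.80 × 0.20 + 0.93 × 0.07)]² / 0.13²
= (1.960 × 0.4833 + 1.036 × 0.4744)² / 0.0169 = 2.0705 / 0.0169 = 122.5, so 123 per arm.

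This matches the plan exactly. It is a calculation for two independent groups, which is also the structure of first-report physician correctness by arm.

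**3. A change rate has no direction**

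Two sets of invented changes, each totalling 20%:
- 15% wrong to right, 2% right to wrong, 3% wrong to a different wrong: net 15 − 2 = +13 points.
- 2% wrong to right, 15% right to wrong, 3% wrong to a different wrong: net 2 − 15 = −13 points.

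**4. Two illustrations of how far this could go**

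Both assume independent errors and a stated degree of trust in each test. Neither assumption is in the documents.

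- *Equal change, unequal tests.* Take 80% and 93%, with physicians always adopting the latest report. Discordance is 0.20 × 0.93 + 0.80 × 0.07 = 0.186 + 0.056 = 24.2% in either order, while correctness moves +13 points in Arm 1 and −13 in Arm 2. Ignoring independence, if every ULDCT error were also a plain-film error, the rate would be 0.20 − 0.07 = 13% in both arms. Changes from one wrong diagnosis to another would add up to 0.20 × 0.07 = 1.4 points under independence.
- *Unequal change, equal tests.* Take 86% for both, full trust in ULDCT and half trust in plain film. Discordance is 2 × 0.86 × 0.14 = 24.1%, so change is 24.1% v 12.0% with no net gain in either arm. At 123 per arm a two-proportion test would be significant about 69% of the time. At plain-film trust 0.6, 0.75 or 0.8 this falls to 48%, 21% or 15%. If 8% of patients were wrong on both tests, discordance would be 2 × (0.14 − 0.08) = 12%, and the figure about 38% at trust 0.5.

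**5. Power of the omitted comparison**

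The documents give no physician accuracy, so these rates are assumed (one-sided 2.5%, 123 per arm):

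| Correct after first report, Arm 1 v Arm 2 | Power |
|---|---|
| 80% v 93% | 85.1% |
| 80% v 90% | 59.4% |
| 80% v 88% | 40.1% |
| 80% v 85% | 17.6% |

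**The case against.** The strongest reply is that this asks for a different estimand. The hypotheses concern the modalities, radiological accuracy is compared with the gold standard, and frequency of change is a direct, if crude, measure of impact on the clinician. The plan never claims to measure physician accuracy. This stands as far as the main hypothesis goes. It does not rescue the aim in Section 4, because an impact whose direction is unknown is not interpretable. Neither the Section 13 between-arm frequency nor the open-ended chi-square sentence in Section 14 mentions the correctness of physicians' diagnoses.

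Several stronger readings are tempting, and the documents do not support them:

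- *That the change comparison will mislead.* Equal change of 24.2% requires Arm 2 physicians to drop the ULDCT diagnosis and adopt plain film alone. Section 5 has the second report in Arm 1 summarise both examinations and lets the radiologist in Arm 2 add to the ULDCT report. Section 13 speaks of a consensus report. If Arm 2 physicians acted on plain film in only a quarter of discordant cases, change would be 24.2% v 6.1%, and the test would detect it with about 98% power.
- *That change is the only physician outcome.* Change in therapy and confidence are also listed. Neither measures correctness.
- *That the data already exist in usable form.* As worded in Section 5, the response formats differ between arms.
- *That randomisation makes the added comparison unbiased.* The trial is open label, and under Section 13 the gold standard draws on the results of all imaging procedures, hence on ULDCT itself.

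**Conclusion.** The gap is real. Physicians' diagnoses are recorded at two points in randomised arms, a gold standard is planned, and no section scores the one against the other. The conclusion that a change frequency cannot by itself show impact on final diagnosis follows from its definition and needs no assumption about trust or error correlation. The scenarios in step 4 of the working show what is possible; they are not predictions.

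The consequence is confined to the secondary, clinical-impact conclusions. A reader might infer that the trial's accuracy result is undermined; it is not, because the primary radiological comparison is planned separately. Nor should the added comparison be sold as an 85%-power test: that figure applies the plan's modality accuracies to physicians, and smaller gains give much less. It is a worthwhile, inexpensive improvement to a secondary analysis.

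**What to change.** In Sections 6 and 14:

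1. Report change in the physician's diagnosis per arm in five categories: wrong to right, right to wrong, wrong to a different wrong, unchanged right, unchanged wrong.
2. Add a secondary outcome: the proportion of physicians' primary diagnoses after the first report that match the gold standard, Arm 1 v Arm 2, with the difference and 95% CI. Present it as an estimate.
3. Ask the same question in both arms (the nine diagnoses plus 'other', with probabilities), amend Section 5 to say so, and define the primary diagnosis as the category given the highest probability.
4. Report a Brier score of the recorded probabilities only if the formats are harmonised in this way.
5. State as a limitation that the gold standard includes ULDCT, so the comparison may favour the ULDCT-first arm.

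The cost is one harmonised response form, SAP wording and one extra table. No additional patients, staff or procedures are needed.

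### The listed physician questions omit planned therapy and further imaging and differ by arm, so the clinical-impact outcomes lack the first-report data they need

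*Combined protocol and SAP*

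**What the plan says.** Every participant has both examinations, and the arms differ only in which is reported first (Sections 5 and 10). Section 5 does not number the arms; I take Arm 1 to be plain film first and Arm 2 to be ULDCT first, in the order listed.

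- Section 5, Arm 1: "Emergency physicians will first receive the report for the plain film of the chest and will be asked for the diagnosis and its probability". After the ULDCT report, diagnosis and probabilities are documented again.
- Section 5, Arm 2: after the ULDCT report, physicians "will be asked for probabilities of the nine most frequent diagnoses in chest-imaging plus" a residual category, and give the same probabilities after the plain-film report.
- Section 6, secondary outcomes: "Frequency of change in (planned) therapeutic course of action by emergency physician" and "Frequency of additional diagnostic imaging needed". Several other outcomes in that list are tied to ULDCT and plain film by name; the further-imaging outcome is not.
- Section 13, on the final treatment decision: "the emergency physician always needs an immediate consensus report on both methods written by a single specialist in radiology". The same paragraph adds: "The frequency with which diagnoses and therapies by radiologists and emergency physicians differ between Arm 1 and Arm 2 will be measured". It does not say at which stage.
- Section 14 gives χ² tests for percentages and a Mann-Whitney U test for diagnostic confidence. It defines no stage or contrast for the secondary outcomes.

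Section 4 states the aim of assessing what each method contributes to the final diagnosis and to changes in therapy.

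**The concern.** In this design only the interval between the two reports separates the modalities. In that interval one arm holds the plain-film report alone and the other holds the ULDCT report alone. Section 5 describes a query in exactly that interval, but planned therapy and further imaging are not among its items. The only treatment decision whose timing is described is the final one, when both arms hold both reports.

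The clinical-relevance aim is at stake. Near-identical final therapy or imaging rates in the two arms could be read as showing that ULDCT has no clinical impact, when the comparison had no means of showing one. The loss cannot be repaired at analysis, because a physician's intention before the second report cannot be reliably reconstructed once that report has been seen.

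The unequal query is a second problem. If Arm 1 physicians name one diagnosis with its probability and Arm 2 physicians score ten categories, then how diagnosis is elicited is confounded with arm for two further secondary outcomes: change in the physician's diagnosis and the physician's diagnostic confidence.

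**Working it through.** **1. What is held and what is asked at each stage**

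| Stage | Report held, Arm 1 | Report held, Arm 2 | Items listed in Section 5 |
|---|---|---|---|
| After first report | Plain film | ULDCT | Arm 1: diagnosis and its probability. Arm 2: ten category probabilities |
| After second report | Both | Both | Arm 1: diagnosis and probabilities. Arm 2: the same ten probabilities |

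Planned therapy and further imaging appear in no cell. Change in planned therapy needs a value in both rows. Further imaging could come from either row, or from later records; Section 6 does not say.

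The unequal query matters even with both rows filled. In Arm 1 a change of diagnosis can be read directly from the named diagnosis. In Arm 2 it needs a rule for when ten probabilities amount to a changed diagnosis, and Section 14 has none. The confidence compared by the Mann-Whitney U test could likewise be a single stated probability in one arm and something derived from ten in the other.

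**2. The plan's own figure**

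Section 14 gives 123 per arm for accuracies of 80% and 93%, one-sided α 2.5%, power 85%. With m = (p1+p2)/2, variance pooled under the null hypothesis and no continuity correction:

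power = Φ( [ |p1−p2|·√n − 1.96·√(2m(1−m)) ] / √(p1(1−p1)+p2(1−p2)) )

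For 0.80 v 0.93, n = 123: (0.13×11.09 − 1.96×0.4833)/0.4744 = 1.042, and Φ(1.042) = 0.851. The stated figure is reproduced. It concerns accuracy; the documents give no rates for therapy or further imaging.

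**3. Outcome taken after both reports**

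Both arms hold the same two reports, so without an order effect p1 = p2. The formula reduces to Φ(−1.96) = 0.025 at any common rate. The test rejects at its own α, whatever either modality would have done alone.

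**4. Further imaging taken after the first report (plain film v ULDCT, assumed rates, n = 123 per arm)**

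- 25% v 10%: (0.15×11.09 − 1.96×0.5373)/0.5268 = 1.159, power 88%
- 30% v 15%: power 81%
- 20% v 10%: power 59%
- 30% v 20%: (0.10×11.09 − 1.96×0.6124)/0.6083 = −0.150, power 44%

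**5. Change in plan from first to second report (Arm 1 v Arm 2, assumed rates, n = 123 per arm)**

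- 15% v 3%: power 91%
- 10% v 2%: power 76%
- 10% v 5%: power 32%

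So the arm comparison is informative at the first report and for first-to-second change, with adequate power only for fairly large differences. After both reports it carries no information on the separate modalities.

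**The case against.** A reader might infer that the plan ties therapy and further imaging to decisions made after both reports, so that the arm comparison can never show what either modality contributes. The documents do not support that.

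- Section 6 gives further imaging no time point; undefined is not the same as after both reports.
- The therapy outcome is worded as a change in a plan, which implies a before and an after. It fits the primary outcome's logic of counting reports changed once the second modality is seen. If plans are recorded after each report, Arm 1 shows what ULDCT adds to plain film and Arm 2 shows what plain film adds to ULDCT.
- The Section 13 sentence concerns the final decision and explains why one radiologist writes both reports. It does not say that no provisional plan is recorded.
- Section 9 has each examination evaluated before the next is performed, so a single-modality stage exists.
- Section 5 is a short arm description, not a data-collection form, and the difference in query wording may be loose drafting.

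All of this stands against the stronger reading. It does not close the gap. Section 5 is the only description of what physicians are asked, it lists the items at both stages, and it omits what these two outcomes need. That the therapy outcome implies a first-report plan makes its absence from the list more important.

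A further objection bears on the remedy. The trial is open label and every participant has both examinations, so a physician asked after the first report whether more imaging is wanted may answer knowing that the other study examination is coming. That is a real limitation and affects how the question should be worded.

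**Conclusion.** The concern holds in a conditional form. If data are collected as Section 5 lists them, change in planned therapy cannot be computed. Therapy or further imaging taken after both reports would then have an expected arm difference of zero apart from an order effect, and a 2.5% chance of a significant result when there is none. Neither outcome would then serve the Section 4 aim. If plans and imaging wishes are recorded after each report, the Arm 1 v Arm 2 comparison is informative.

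The different query by arm, if carried out literally, would also confound the comparison of physician diagnosis change and confidence.

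Power for a first-report contrast at 123 per arm runs from 44% (30% v 20%) to 88% (25% v 10%) in the four scenarios shown. It rests wholly on assumed rates, and these outcomes were not used to size the trial. Only secondary outcomes are affected; the retrospective accuracy comparison is untouched. The change should still be made, because missing first-report answers cannot be recovered later.

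**What to change.** - **Section 5:** use one identical form in both arms, including the same diagnosis items. Add two items: planned therapy, and whether further imaging is wanted and which. Complete the form after the first report, before the second is shown, and again after the second. Word the first-report imaging item as if no second study examination were available.
- **Section 6:** define change in planned therapy as first v second answer within patient. Define further imaging as the first-report answer. Report the second-report answers descriptively.
- **Section 14:** state that both are compared between Arm 1 and Arm 2 by the χ² test. This is valid because each patient contributes one value and the arms are independent. State that power for these outcomes depends on rates not yet known.

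The cost is two items on a query already made twice per patient, a little more physician time, and short edits to three sections. The hypothetical wording reduces the influence of knowing that another examination is coming but cannot remove it in an open-label trial, so it should be stated as a limitation.
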